The VHA DSS data files comprise a longitudinal, secondary relational database combining selected clinical and cost data. The DSS provides a mechanism for integrating expenses, workload, and patient utilization. DSS information supports process and performance improvements by measuring quality of care, clinical outcomes, and financial impact. Within a fiscal year, periodic rollups of production data are performed to produce year-to-date, non-destructive examinations.

DSS Clinical National Data Extract

- Laboratory Results: laboratory test results for a specific list of tests (inpatient and outpatient)
- Pharmacy: pharmacy prescription utilization and costs (inpatient and outpatient)

VA Vital Status Files

The VHA Vital Status File (VSF) contains the date of death for veterans and eligible non-veterans who have received care from the VHA since 1992, have enrolled in the VHA, or have received compensation or pension benefits from the VHA since 2002. The VHA VSF file is updated quarterly.

Sources for vital status available to the VA include the VA Beneficiary Identification and Record Locator System, the Death Master File from the Social Security Administration (SSA), patient treatment file, and Medicare vital status. The primary source for dates of death in the Vital Status file is the SSA Death Master File. The impetus for the development of the VHA VSF was the VA Information Resource Center's (VIREC) Veterans Administration National Death Index (NDI) Data Merge Project. This work was supported by funding from the Health Services Research and

[2019-8636] Observational Study Protocol

Development Service (SDR 03-157) and VIREC (SDR 98-004). The project compared the dates of death from sources available within the VA to those obtained from the NDI, a repository of data from death certificates that is considered the gold standard for mortality data in the United States. The study found that using a combination of the available death data sources in the VA resulted in death ascertainment nearly as complete as using the NDI.

The stability of VHA data sources allows for superior analysis of the continuity of care of patients over multiple years.

Data Limitations

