5.3. Study Population

5.3.1 Selection Criteria

U-500R Syringe Initiators [Index Event a]

Inclusion Criteria

Patient will be included if they:

- had ≥ 1 prescription claim for U-500R vial during the identification period (VHA: 01JAN2014–30JUN2017; Truven: 01JUL2014–30JUN2017), with the first prescription claim for U-500R vial designated as index Event a (U-500R syringe initiation), and the date designated as the index date;
- had ≥ 2 claims with an ICD-9/10-CM code (Appendix 1) for T2DM in any position (primary/secondary) at any time prior to the index date;
- were aged ≥ 18 years on the index date;
- had continuous health plan enrollment with medical and pharmacy benefits for ≥ 9 months pre- and post-index event;
- had ≥ 1 prescription claim for any insulin other than U-500R in the pre-index period;
- had ≥ 1 HbA1c measurement within 90 days pre-index or 30 days post-index event;
- had ≥ 1 HbA1c measurement after the 30-day post-index period at any time in the 9-month post-index period;

[2019-8636] Observational Study Protocol

- had claims indicating TDD >180 in the post-index period;
- had claims indicating TDD >180 in the pre-index period; and

Exclusion Criteria

Patient will be excluded if they:

- had both T1DM and T2DM, had no oral anti-diabetic drug (OADs; Appendix 1) other than metformin, and the ratio between the number of T1DM and T2DM claims >0.5 at any time in the study period (VHA: 01APR2013–31MAR2018; Truven: 01JUL2013–30JUN2018);
- had previous use of U-500R in the 9-month pre-index period;
- had ≥ 1 claim with an ICD-9/10-CM code (Appendix 1) for secondary diabetes, gestational diabetes, diabetes complicating pregnancy, childbirth, puerperium, or non-clinical diabetes at any time during the 9-month pre-index period;
- had claims indicating pump use (Appendix 2) in the 9-month post-index (follow-up) period;
- had claims indicating TDD above 2000 units/day at any time in the pre-index or post-index periods; or
- had claims indicating insulin use other than U-500R in the post-index period.

U-500R Kwikpen Initiators [Index Event **b**]Inclusion Criteria

Patient will be included if they:

- had ≥ 1 prescription claim for U-500R Kwikpen administration during the identification period (VHA: 01JAN2014–30JUN2017; Truven: 01JUL2014–30JUN2017), with the first prescription claim for U-500R Kwikpen administration designated as Index Event **b**, and the date designated as the index date;

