5.4 Time Periods

The study period will range from 01APR2013–31MAR2018 for VHA, and 01JUL2013–30JUN2018 for Truven MarketScan claims. The identification period will be 01JAN2014–30JUN2017 for VHA, and 01JUL2014–30JUN2017 for Truven MarketScan claims. The pre-index and post-index periods will be 9 months for the VHA and 12 months for the Truven MarketScan database, respectively (Figures 1-3).

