5.5 Variables/Measures

Table 2 presents the study variables and operational definitions.

Table 2 Variables and Definitions

Variable	Source	Definition
Exposure		
Insulin use	Truven: Outpatient pharmacy claims table VHA: Pharmacy file	Index Event a : any insulin use other than U-500R in the pre-index and high-dose U-500R syringe use in the post-index period Index Event b : any insulin use other than U-500R in the pre-index and high-dose U-500R Kwikpen use in the post-index period Index Event c : any insulin use other than U-500R in the pre-index and high-dose U-500R Kwikpen/syringe use in the post-index period
Patient Characteristics*		

[2019-8636] Observational Study Protocol

Variable	Source	Definition
Age	Truven: Inpatient service table, outpatient service table, outpatient pharmacy claims table VHA: Enrollment file	Age will be retained in the dataset as a continuous variable for groups aged 18-25, 26-35, 36-45, 46-55, 56-64, and ≥ 65 years.
Sex	Truven: Inpatient service table, outpatient service table, outpatient pharmacy claims table VHA: Enrollment file	A flag will be created for male and female patients.
Race (only VHA)	VHA: Enrollment file	A flag will be created for white, black, and other race patients.
US Region (only Truven)	Truven: Inpatient service table, outpatient service table, outpatient pharmacy claims table	A flag will be created for patients residing in the Northeast, Northcentral, South, and West US regions.
Medicare eligibility (only Truven)	From Truven	A flag will be created for patients who are enrolled in Truven Medicare.
Body mass index (BMI)	VHA: Vital Status file	BMI on the index date will be calculated and reported as a continuous variable.
Quan-Charlson comorbidity index (CCI) score ²⁶	Truven: Inpatient service table, outpatient service table VHA: Inpatient and outpatient files	Quan-CCI score will be constructed using enhanced ICD-9/10-CM codes for 17 different comorbid conditions.
Individual Comorbidities ²⁷	Truven: Inpatient service table, outpatient service table VHA: Inpatient and outpatient files	A flag will be created using ICD-9/10-CM codes (Appendix 1) for patients diagnosed in the pre-index period with any of the following individual comorbidities: retinopathy, nephropathy, neuropathy, coronary artery disease, peripheral vascular disease, congestive heart failure, hypertension, depression, obesity, or malignant tumor.
Health Economics Outcomes Research (HEOR) Outcomes		

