Concomitant medications ^{28,29,30}	Truven: Outpatient pharmacy claims table VHA: Pharmacy file	A flag will be created for patients prescribed the following antihyperglycemic agents (AHA):

[2019-8636] Observational Study Protocol

Variable	Source	Definition
		thiazolidinediones, sulfonylureas, biguanides, meglitinides, alpha-glucosidase inhibitors, DPP-4 inhibitors, SGLT-2 inhibitors, bile acid sequestrants, fixed-dose combinations, GLP-1 receptor agonists, and amylin agonists (Appendix 1).
HbA1c ³¹	VHA: Lab file	The HbA1c value in the pre-index and post-index period for each index event will be reported. Pre-index HbA1c will be the HbA1c measurement -90/+30 days of the index date. For patients with multiple HbA1c measurements within this period, the measurement taken closest to the index event date will be reported as the pre-index HbA1c value. The post-index HbA1c value will be the farthest HbA1c measurement taken in the time period after the 30 day-post index event date.
Change in HbA1c		The change in HbA1c will be defined as the difference in the pre-index and post-index HbA1c values.
Hypoglycemic events	Truven: Inpatient service table, outpatient service table VHA: Inpatient and outpatient files, Lab file and Pharmacy file	Hypoglycemia events in the pre- and post-index periods will be evaluated using the ICD-9 codes from the Ginde algorithm (Appendix 1), ³² the presence of a cutoff of blood glucose ≤ 70 mg/dL, or any evidence of intramuscular glucagon administration (Appendix 1). Hypoglycemia events that occurred on or after the index date will be considered the follow-up hypoglycemia event; and hypoglycemia event occurred on or prior to - 1 day of the index date will be considered as the pre-index hypoglycemia event. The number of hypoglycaemia events per patient per year (PPPY) will be reported in both the pre-and post-index periods.

[2019-8636] Observational Study Protocol

Variable	Source	Definition

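### The post-index other-insulin exclusion does not limit VHA insulin records to outpatient dispensing, so insulin given in hospital could remove patients and tilt the hypoglycemia comparison toward U-500R

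*Protocol*

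**What the plan says.** Protocol Section 5.3.1 excludes, with the same wording for Index Events a, b and c, anyone who "had claims indicating insulin use other than U-500R in the post-index period". It sets no outpatient limit and makes no exception for hospital days. Before index the requirement runs the other way: the patient must have "had ≥ 1 prescription claim for any insulin other than U-500R in the pre-index period".

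Table 2 (Section 5.5) gives the source of insulin use as "Truven: Outpatient pharmacy claims table VHA: Pharmacy file". The same pair of sources is listed for TDD, ADD and adherence. Section 5.2 describes one VHA pharmacy source, in the DSS Clinical National Data Extract: "Pharmacy: pharmacy prescription utilization and costs (inpatient and outpatient". Figure 4 describes it in the same way.

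Hypoglycemia in VHA is drawn from "VHA: Inpatient and outpatient files, Lab file and Pharmacy file", and Table 2 adds: "The number of hypoglycaemia events per patient per year (PPPY) will be reported in both the pre-and post-index periods". On follow-up, Section 5.4 states: "The pre-index and post-index periods will be 9 months for the VHA and 12 months for the Truven MarketScan database, respectively".

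**The concern.** The exclusion is meant to secure insulin monotherapy with U-500R. Another insulin given on a ward during a short stay is not a change in the outpatient regimen, yet the wording lets it count as other insulin use in VHA. Truven names an outpatient table, so the same event could not exclude a Truven patient.

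The effect is one-sided in time. Other insulin is an entry condition before index, so inpatient insulin in a pre-index admission excludes nobody. The same record after index removes the patient. Cohort membership then depends on a post-exposure event, admission, that may accompany hypoglycemia. Hypoglycemia is Secondary Objective 2a and the only adverse event defined in Section 7.1. Its analysis is repeated in the elderly subgroup, for whom Section 3 says safety has not been explicitly studied.

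The unrestricted file also feeds total insulin units. TDD decides cohort entry (>180 units/day in both periods) and membership of the 201–300 subgroup, so inpatient records could misclassify patients there too. The documents do not allow the direction of that second effect to be worked out.

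**Working it through.** **No figure to reproduce.** The protocol gives no hypoglycemia rate, admission rate or frequency of inpatient insulin. Table 3 holds feasibility counts only (647 Kwikpen, 1,766 syringe) and does not show how many patients the other-insulin rule removes. The check is therefore a trace of the text followed by an illustration under no true change.

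**Trace.**
1. The rule names insulin use other than U-500R, without limiting the setting (5.3.1).
2. Insulin use in VHA comes from the pharmacy file, again without limit (Table 2).
3. The VHA pharmacy source described holds inpatient and outpatient records (5.2, Figure 4).
4. The corresponding Truven source is outpatient only (Table 2).
5. VHA hypoglycemia counts inpatient diagnoses, and laboratory glucose of 70 mg/dL or below (Table 2). Section 5.2 says the laboratory extract includes inpatients.

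**Formula.** Assume each patient has the same underlying event rate λf before and after index, with f a patient-specific frailty, and that events are independent given f. Let s be the share of events that occur in admissions, and q the probability that such an admission carries a recorded other insulin. A patient is dropped if any post-index admission does so. Among retained patients:

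- pre-index rate = λ · E[f | retained]
- post-index rate = λ(1 − sq) · E[f | retained]
- ratio = 1 − sq for all events, and 1 − q for events in admissions alone

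The frailty term cancels, so the loss of the removed patients' pre-index events is already accounted for.

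**Expected post/pre ratio for all events, no true change (s and q assumed):**

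| s | q = 0.25 | q = 0.50 | q = 0.75 | q = 1.00 |
|---|---|---|---|---|
| 0.02 | 0.995 | 0.990 | 0.985 | 0.980 |
| 0.05 | 0.988 | 0.975 | 0.963 | 0.950 |
| 0.10 | 0.975 | 0.950 | 0.925 | 0.900 |
| 0.20 | 0.950 | 0.900 | 0.850 | 0.800 |

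For events in admissions alone the ratio is 0.75, 0.50, 0.25 and 0.00 across the same values of q. A simulation (2,000,000 patients per setting, gamma frailty with variance 1, 0.75 years per period) agreed to within 0.01. With q = 0, which is the outpatient-only rule, it gave 1.00.

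**Patients removed.** With that frailty and a rate r per patient-year of events in admissions, the share dropped is 1 − 1/(1 + 0.75rq).
- r = 0.02, q = 0.25: 0.00375/1.00375 = 0.37%, about 2 of 647 or 7 of 1,766.
- r = 0.10, q = 1.00: 0.075/1.075 = 6.98%, about 45 of 647 or 123 of 1,766.

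The rates r are assumptions. Admissions without hypoglycemia would remove further patients.

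**The case against.** The strongest reply is that the protocol never says inpatient records count. The rule speaks of claims. Section 3 says the dose observed in claims data reflects what the patient purchased, the data limitations in Section 5.2 refer to claims for filled prescriptions, and Table 2 builds PDC from prescription claims. An inpatient dose is neither purchased nor filled by the patient. This stands: a reader might infer that hospitalized patients will be dropped, but the documents show only that they could be. None of those phrases is a definition, however, and someone programming from Table 2 has no instruction to filter the VHA file.

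It can also be said that record selection belongs in the analysis plan, which is not at hand. But eligibility and data sources are already fixed here. The note in Section 5.3.1 lists how Truven selection differs (no HbA1c criterion, 12-month periods) and does not mention this difference.

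Three stronger readings are tempting and fail:
- That only post-index events are lost. Exclusion removes the whole patient, including pre-index events.
- That a comparison of serious hypoglycemia is biased. No severity or hospitalized-event endpoint is defined; Objective 2a uses total events.
- That the spurious fall is much larger. Suppose 15% of patients are admitted, 90% of them receive another insulin, and admitted patients hold 50% of post-index events. Holding the pre-index rate fixed gives (1 − 0.45)/(1 − 0.135) = 0.64. If those patients also held 30% of pre-index events, the result is 0.55/0.73 = 0.75; at 50% it is 1.00. All these inputs are assumed, and nothing in the protocol supports them.

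**Conclusion.** The concern holds in conditional form, and for VHA only. The wording permits inpatient insulin to trigger the post-index exclusion and to enter TDD, ADD and PDC, while Truven is confined to outpatient claims. If inpatient records are counted, selection is one-sided in time and the total-event comparison is biased toward U-500R looking safer.

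The size cannot be derived from the documents. Over the assumed range the bias in the all-event ratio runs from negligible (0.995) to a spurious 20% fall (0.80); it is larger for events in admissions, which the plan does not analyze separately. This rests on equal true rates in both periods, events independent given a stable patient frailty, and assumed s and q. Because inpatient glucose values count as events, s is not confined to admissions caused by hypoglycemia.

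The protocol's own caveat in Section 3, that the rule may remove early discontinuers who switch, is offered as a reason not to study persistence and does not cover this effect.

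**What to change.** In Section 5.3.1, for all three index events, and in Table 2, state that VHA insulin use for the other-insulin exclusion and for TDD, ADD and PDC means outpatient dispensing only, matching Truven. Keep and flag patients whose only other post-index insulin is an inpatient record, and report their number.

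The cost is a sentence in each place and one filter in the cohort program. The monotherapy restriction stays intact. The downside is that a few retained patients will have had brief inpatient exposure to another insulin, which the flag makes visible. If outpatient dispensing was always intended, only the wording changes.

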FDA approved label. In this study, we will evaluate patient characteristics, treatment patterns, treatment compliance, treatment outcomes (including HbA1c and hypoglycemia), and insulin-related out-of-pocket pharmacy costs among T2DM patients who initiated U-500R high-dose, defined by having an average TDD >180 units/day both before and after U-500R initiation, insulin monotherapy with U-500R after initiation with no evidence of pump use (instead of 200 units/day).

As pointed out by Hood et al 2015, compliance may be an issue among patients who were on high dose U-100 insulin. However, there are multiple aspects to the medication compliance.¹⁵ According to Cramer et al 2008, compliance “refers to the degree or extent of conformity to the recommendations about day-to-day treatment by the provider with respect to the timing, dosage, and frequency.”²² It may be defined as “the extent to which a patient acts in accordance with the prescribed interval, and dose of a dosing regimen.” Since insulin treatment is required for patients on a daily basis, for practical purpose, adherence is measured by proportion of days covered (PDC). Dosage, calculated as both total daily dose (TDD) and average daily dose (ADD), is another compliant aspect that is critical to the outcomes of insulin treatment. However, with claims data, the observed dosage reflects only the amount of insulin purchased by a patient, not the actual dose taken or prescribed. Nevertheless, comprehensively comparing PDC and TDD/ADD together with treatment outcomes (HbA1c, hypoglycemia) before and after U-500R initiation will provide a picture on how U-500R might affect the medication compliance and its impact on outcomes. Since this study focuses on only high-dose cohort, we will refrain from studying medication persistence defined as “the duration of time from initiation to discontinuation of therapy.” This is because, to ensure only patients with U-500R insulin monotherapy were included in the high-dose cohort, the exclusion criteria used will remove any patient that had more than one insulin use in the post-index period and inadvertently remove some patients who had early U-500R discontinuation and switched to other therapies. Medication persistence has been studied in the full RWE cohort.

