The treatment patterns and outcomes of two sub-groups are of great interests. The first subgroup is the elderly. Given the highly concentrated nature of U-500R, physicians have hesitation in using U-500R with their elderly patients. Even though elderly accounted for about 50% of the U-500R initiators in an ongoing study (full RWE cohort), no studies have explicitly examined the safety and efficacy of U-500R in elderly. Information on the effectiveness and safety of U-500R among elderly will be valuable to HCPs and patients. The other subgroup of interests are those whose U-500R daily dose is in the range of 201-300 units/day. While most physicians are confident with the use of U-500R when patients insulin needs exceed 300 units/day, this is not the case in the range of 201-300 units for some physicians. Currently only less than 20% of patients on 201-300 units/day insulins use U-500R (internal data-on-file). Therefore, it is important to understand the compliance, effectiveness, and safety among those who were on 201-300 units/day of U-500R insulin. Additionally, the U-500R Kwikpen was launched in 2016. Therefore, a 9-months pre- and post-index period will be applied in the VHA to ensure adequate sample size due to the recent launch of the Kwikpen. Since VHA does not have reliable cost data, Truven database is used to understand out-of-pocket costs and will be assessed using a 12-months pre- and post-index period to ensure deductibles are properly captured for all patients.

The aim of this study is to provide a comprehensive understanding of U-500R in high-dose cohort (defined by having an average TDD of >180 units per day, with no additional insulin used concomitantly with U-500R or pump use), including compliance, effectiveness, safety, and out-of-pocket costs, rather than just one particular aspect of U-500R. Ideally, an integrated database with both claims and EMR data will be needed for such a study. Unfortunately, while VHA database is an integrated claims and EMR database, it lacks reliable costs data. As a result, out-of-pocket costs aspect will be examined separately using IBM MarketScan data.

[2019-8636] Observational Study Protocol**4. Objectives****4.1 Research Objectives****Research Objective 1: Treatment Patterns**

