- had ≥ 1 HbA1c measurement after the 30-day post-index period at any time in the follow-up period;
- had claims indicating TDD >180 in the post-index period; and
- had claims indicating TDD >180 in the pre-index period

[2019-8636] Observational Study ProtocolExclusion Criteria

Patient will be excluded if they:

- had both T1DM and T2DM, had no OADs (Appendix 1) other than metformin, with the ratio between the number of T1DM and T2DM claims >0.5 at any time in the study period (VHA: 01APR2013–31MAR2018; Truven: 01JUL2013–30JUN2018);
- had previous use of U-500R in the 9-month pre-index period;
- had ≥ 1 claim with a ICD-9/10-CM code (Appendix 1) for secondary diabetes, gestational diabetes, diabetes complicating pregnancy, childbirth, or puerperium, or non-clinical diabetes at any time during the pre-index period;
- had evidence of pump use (Appendix 2) in the follow-up period;
- had claims indicating TDD above 2000 units/day at any time in the pre-index or post-index periods; or
- had claims indicating insulin use other than U-500R in the post-index period.

Note:

- All high-dose U-500R patients will be defined by having an average TDD of >180 units per day, with no additional insulin used concomitantly or no U-500R pump use.
- Since the Truven claims database does not include lab data, the ≥ 1 HbA1c criterion will be removed from the selection criteria while using this database.
- For analysis conducted using the Truven claims database, the pre-index period and the post-index period will be 12 months instead of 9 months.
- The corresponding ICD-9/10 codes for all the diagnoses and the NDC codes for the insulin treatments are provided in Appendix 1.

Subgroup analysis:

- Elderly (≥ 65 years) patients among each of the high-dose U-500R Kwikpen, high-dose U-500R syringe, and any high-dose U-500R initiator cohorts will be flagged, and a subgroup analysis will be performed comparing the treatment patterns and outcomes (HbA1c and hypoglycemia) before and after U-500R initiation.
- Patients with a TDD of 201-300 units in the post-index period among each of the high-dose U-500R Kwikpen, high-dose U-500R syringe, and any high-dose U-500R initiator cohorts will be flagged, and a subgroup analysis will be performed comparing the treatment patterns and outcomes (HbA1c and hypoglycemia) before and after U-500R initiation.

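### The cohort and its dose subgroups are selected on post-initiation information: TDD change inside the dose bands largely reflects the cut, and the HbA1c, hypoglycemia and PDC results cover only patients who stayed on high-dose U-500R monotherapy

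*Protocol*

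**What the plan says.** For all three index events, Section 5.3.1 includes a patient only if they "had claims indicating TDD >180 in the post-index period" and also "had claims indicating TDD >180 in the pre-index period". It further requires that they "had continuous health plan enrollment with medical and pharmacy benefits for ≥ 9 months pre- and post-index event" (12 months in Truven, by the note to that section) and, in VHA, that they "had ≥ 1 HbA1c measurement after the 30-day post-index period at any time in the 9-month post-index period". A patient is excluded who "had claims indicating insulin use other than U-500R in the post-index period" or who shows pump use after the index date.

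The dose subgroups are "Patients with a TDD of 201-300 units in the post-index period among each of the high-dose U-500R Kwikpen" and the corresponding syringe and any-U-500R cohorts, with an optional band above 300.

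Table 2 (Section 5.5) defines the change in observed TDD as a study variable, and Primary Objective 1 asks for before/after differences in it, including within the dose subgroups. Section 6.4.1 tests continuous before/after values by paired t-test, and Section 6.3 sets two-sided p<0.05 without multiplicity adjustment. The same approach is repeated in the subgroups for adherence, HbA1c and hypoglycemia.

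Section 3 concedes that the monotherapy rule will "inadvertently remove some patients who had early U-500R discontinuation and switched to other therapies", and for that reason drops persistence as an outcome. It does not carry the point over to TDD, PDC, HbA1c or hypoglycemia. The data limitations in Section 5.2 do not mention it.

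**The concern.** A before/after comparison is easy to interpret when the patients are fixed by what is known at the index date. Here membership depends on what happened afterwards, and this works in two ways.

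- **TDD.** The selection variable is the outcome. A band cut on post-index TDD fixes the second member of each pair and leaves the first to vary, so a mean difference arises even if nothing changed. A paired t-test against zero does not answer a clinical question there.
- **HbA1c, hypoglycemia and PDC.** Their values are not selected on, but events linked to them are: dose during follow-up, return to another insulin, and remaining enrolled. A patient who added another insulin because control was poor, or who left the plan or died, contributes nothing. Within the dose bands, dose may also have been lowered after hypoglycemia or raised for non-response, so contrasts are open to reverse causation.

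The mixed models in Section 6.4.1 adjust for observed TDD but cannot bring back excluded patients. Both primary objectives and the only safety outcome rest on this cohort, and Section 3 presents the study as informing effectiveness and safety.

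**Working it through.** The Protocol has no figure of its own to reproduce on this point, because Table 3 gives counts only. The check is a simulation of paired TDD.

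**Inputs from Section 3.** Kwikpen TDD 188 ± 72, median 176; 62% at or below 200 before initiation; 27% at or below 200 after; mean rise of more than 80 units/day.

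**Assumptions.** The 188 ± 72 is pre-index (the Protocol does not say when it was measured). TDD is lognormal. The 27% is a marginal proportion. The pre/post correlation r is 0.3 to 0.7.

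1. Pre-index spread: sigma = sqrt(ln(1 + (72/188)²)) = 0.370, median 188/exp(0.370²/2) = 175.6.
2. Consistency: P(TDD ≤200) = Φ(ln(200/175.6)/0.370) = 63.8%, against 62% stated. The inputs fit together.
3. Null case: post-index TDD has the same distribution as pre-index TDD.
4. Change case: post-index mean 188 + 80 = 268, with sigma solved so that 27% are ≤200. This gives sigma 0.367 and median 250.5.
5. Apply pre >180 and post >180, then the post-index bands. Mean post minus pre, in units/day:

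| Case | Group | r=0.3 | r=0.5 | r=0.7 |
|---|---|---|---|---|
| Null | post 201-300 | -10.6 | -10.0 | -6.6 |
| Null | post >300 | +93.9 | +76.5 | +54.2 |
| Null | whole cohort | 0.0 | -0.1 | 0.0 |
| +80 | post 201-300 | +8.3 | +16.7 | +30.5 |
| +80 | post >300 | +139.2 | +135.5 | +130.4 |
| +80 | whole cohort | +63.7 | +73.5 | +84.1 |
| +80 | pre >180 only | +47.3 | +63.5 | +80.1 |
| +80 | removed by the post >180 rule | 11.7% | 7.4% | 3.2% |

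Fitting the lognormal by mean and median instead (sigma = sqrt(2 ln(188/176)) = 0.363) gives null values of -9.6, -9.5, -6.2 and +93.4, +76.4, +53.1. The two fits agree to about one unit. The rounded ranges used elsewhere in this point (-6 to -10 and +54 to +93) lie within their spread.

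6. Regrouping on pre-index TDD instead, null case. Within the cohort, the >300 band shows about -53 to -93 and the 201-300 band about +6 to +10. Without the post-index >180 rule, >300 shows about -59 to -125 and 201-300 about -14 to -34. This is the mirror image, and for 201-300 without the post-index rule it is larger than the artefact it would replace.

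7. HbA1c and hypoglycemia: what-if only, all inputs assumed.
   - HbA1c: SD of change 1.5, 10-30% excluded, odds ratio of exclusion 1.25 to 2 per +1 point of HbA1c change. A true change of 0 then appears as -0.05 to -0.39. At odds ratio 1 there is no bias. At the reciprocal odds ratios the sign reverses by symmetry.
   - Hypoglycemia: 0.5 to 2 events per year, exclusion 10-30 percentage points more likely after a post-index event. A true change of 0 then appears as about -0.03 to -0.10 events per patient-year. Section 3 cites a real-world change of +0.21 per year.

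**The case against.** The other side has real weight.

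- **Scope.** The aim is to describe label-consistent use. Section 3 says that earlier studies covered all initiators and that a parallel study covers lower doses. Describing sustained high-dose monotherapy is legitimate, and the cohort can stay. But the earlier full cohort had 62% at or below 200 units/day before Kwikpen, so it does not describe high-dose initiators, and the planned tests go beyond description.
- **The dose bands.** A reader might infer, from the remark that "most physicians are confident with the use of U-500R when patients insulin needs exceed 300 units/day", that the bands should be defined by need before initiation. The same paragraph defines the subgroup by U-500R daily dose. Prior U-500R use in the pre-index period is barred, so that dose is necessarily post-index. Pre-index regrouping would also bring in mirror-image regression to the mean (step 6). This objection stands.
- **Whole-cohort TDD.** A reader might infer that the overall TDD change is biased too. The >180 rule applies before and after, and the null change is about 0. In the +80 case the post-index rule moves the mean by 4 to 16 units/day relative to pre >180 alone, and the cohort result lies on either side of 80 depending on r. This objection stands.
- **Optional analysis.** The largest artefact is in the >300 band, which is optional. That is true; the planned 201-300 band shows the smaller one.
- **Reporting detail.** Attrition tables and conclusion wording often sit in a SAP or report. That is fair for their layout, but the Protocol itself fixes the filters, the tests and the narrow caveat.

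**Conclusion.** The point holds in a limited form. For TDD, selection is directly on an outcome, and a significant TDD change inside a post-index dose band would be largely produced by the cut: about -6 to -10 units/day for 201-300 and +54 to +93 for >300 with no true change. These sizes rest on the assumed correlations, the lognormal shape, and reading 188/176 as pre-index figures. That the cut creates a difference does not depend on their exact values.

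For HbA1c, hypoglycemia and PDC, the results apply only to patients who stayed on high-dose U-500R monotherapy and stayed enrolled. A reader might infer that the results must therefore favour U-500R. That is plausible, since switchers for poor control are removed. The document does not establish it: requiring sustained TDD above 180 could also remove good responders whose dose fell and keep patients at higher hypoglycemia risk. Neither direction nor size can be derived from the Protocol. The present defect is that Section 3 recognises the mechanism for persistence and is silent for every outcome it retains.

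**What to change.** 1. Keep the 201-300 and optional >300 post-index subgroups as descriptive. Do not test TDD change within them, and state that their HbA1c and hypoglycemia contrasts are open to reverse causation. Do not regroup on pre-index TDD to study TDD change.
2. Add a supplementary HbA1c and hypoglycemia analysis in all initiators with pre-index TDD >180 who meet the other pre-index criteria, without the post-index TDD, other-insulin and full-enrolment filters. Use observed person-time for hypoglycemia. Show the number removed by each post-index filter, with the HbA1c and hypoglycemia data available for them.
3. Extend the Section 3 caveat to HbA1c, hypoglycemia, PDC and TDD, and word conclusions from the current cohort as applying to sustained high-dose U-500R monotherapy.

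The cost is programming and one more set of tables from data already held. The drawback is that the added cohort includes patients who later leave high-dose monotherapy, so it answers a different question and should be labelled so.
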